Thus, the innovative idea of simply drinking sodium bicarbonate solutions to induce minor changes in blood pH has been proposed.[21] This idea suffers from two major limitations. First, the pH change required to have significant effect on disrupting the RBD is likely to be too great to safely achieve in blood—a rule of thumb is at least 1 pH unit.[23] Second, even if this could be achieved the expression of ACEr is on the apical (lumen) surface of epithelial cells not the basolateral (plasma) side.[16] However, neither of these are problems for the kidney. Urine pH

is normally 5.5-6.5 (not too dissimilar to alveolar fluid—6.4-6.8[24]) and can be easily and safely manipulated. In fact, urine alkalinization protocols have been used for decades to reduce renal toxicity from various compounds (especially chemotherapy) and are recommended by US and European toxicology societies.[25] Here, the strategy will be deployed not for ion trapping but to inhibit the virus from infecting RTEC. Alkalizing the urine using IV sodium-bicarbonate solution to pH of 7.5 or more can be easily and safely achieved. Acetazolamide can also be added if systemic alkalemia is an issue.[25] An additional advantage of this approach is that it is unlikely to interfere with other interventions that can be studied in these patients (e.g. steroids) which are directed at the lungs.

5. Approach

We will conduct a pragmatic RCT using alkalinization of urine such that most ICU COVID-19 positive patients can be enrolled. Both specific aims will be achieved by the conduct of the trial yet both are independent. The statistical analysis plan for each aim will detail the specific endpoints and hypotheses being testing.

Trial overview: Study inclusion and exclusion criteria are provided in Table 1.

Study design: Open-label randomized trial (1:1) comparing urine alkalinization to standard care. The study will test both feasibility and safety (aim 1) as well as efficacy (aim 2).

Study Management: Study personnel will identify patients and obtain video-enabled informed consent from patients or legally authorized representatives; collect study data and ensure sample collection, processing and storage. The patient's bedside nurse will perform urine pH measurement (dipstick) and deliver the study drug. The study is open-label to facilitate safety and allow for any management of complications (e.g. calcium supplementation).

Table 1. Inclusion/exclusion Criteria

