Inclusion Criteria	Exclusion Criteria
Confirmed COVID-19 +	Stage 3 AKI by KDIGO criteria
Admission to ICU or step-down units at WVU	CKD stage 4-5
Foley catheter* and central line (or PICC) in place	Contraindications to Na bicarbonate therapy (e.g. met. alkalosis, severe heart failure)
Age ≥ 18 y	Urine pH > 7.0
	ECMO Patients

*Foley Catheter can be removed 72 hours after enrollment if appropriate documentation of urine output can be maintained

Urine alkalinization may also increase the elimination of certain drugs including hydroxychloroquine. We do not intend to exclude patients taking these drugs but it will be discussed in the consent form and with the treating physicians.

Intervention: The intervention is a modification/simplification of a standard protocol used for decades for the treatment of various drug toxicities (e.g. salicylate) or to mitigate kidney damage from chemotherapy.[25] Simplifications are intended to tailor the intervention to the management of COVID-19 patients and reduce or eliminate any additional staff exposure. We will continue urine alkalinization for 10 days or until patient is discharged from ICU or step-down unit or until the stage 3 AKI or a safety endpoint is reached. Urine pH will be measured at POC by dipstick. The major elements of the interventional protocol are shown in Table 2. Note, much of the monitoring (e.g. blood gases, calcium) is already performed for routine care. The protocol simply ensures that these measurements are timed to maximize patient safety and minimize burden on bedside nurses. The protocol has been developed with input from [name], Professor and Vice Chair for Research in the Department of Critical Care Medicine at the University of Pittsburgh.

Table 2. Protocol highlights
Sodium bicarbonate 225 mmol (225 mL of an 8.4% solution) intravenously over 1h
Recheck urine pH (dipstick) in 2-4 hours (from start of infusion)
Repeat boluses of intravenous sodium bicarbonate to achieve urine pH ≥ 7.2
Monitor urine pH every 2-4 hours until target is reached and then q6-8 hours
Sodium bicarbonate 8.4% solution should not exceed 900 ml (4 boluses) in 24h
Monitor plasma sodium, potassium, calcium every 12 hours and Acid-base status at least every 24 hours (Note: Arterial pH should not be > 7.50 , or venous > 7.55)
Acetazolamide (Diamox) can be administered at physicians' discretion to control systemic alkalinization and to help avoid fluid accumulation.

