Avoid fluid accumulation. If urine output does not increase to compensate for the increased fluid (it will in most cases, especially if kidney is protected), Lasix or Diamox can be added.
*If fluid balance cannot be maintained within +1L in 24 hours – protocol will be halted and resumed only if either the fluid balance can be correct to within +500mL in 24 hours or if the primary team decides that the patient has clinically appropriate fluid balance.

Data

collection: Information will be collected about patient demographics – date of birth, age, sex, race, weight, height, co-morbidities including but not limited to diabetes, hypertension, heart failure, coronary artery disease, previous cardiac surgeries, chronic kidney disease, cancers. Given the long history and familiarity with urine alkalinization, potential adverse effects (e.g. metabolic alkalosis, hypocalcemia) are well known. Data about renal function (creatinine, urine output, daily ins and outs), basic metabolic panel, blood gas, home medications, medications given during hospital stay and chart review to identify any relevant complications will also be performed. The provider survey will be performed using an online survey instrument and a link will be emailed to the provider to complete.

Sample collection: We will collect urine samples (1 before, 1 at 24 hours and 1 at 48 hours) from initiation of the protocol. Urine samples will be collected, processed and stored in accordance

with EH&S requirements for COVID-19 samples. At a later date and using alternative funding, we plan to analyze these samples for additional biomarkers either at WVU or at partner institution(s) in that study.[26] These biomarkers measure the cellular stress in the kidney[27] and will be examined in an ancillary study. The samples will be stored initially at the laboratories in WVU and then shipped to partner institution(s) for further testing of urine biomarkers as detailed above.

Statistical analysis: Descriptive statistics will be used for reporting: continuous variables expressed as median and interquartile range while categorical variables as frequency and percentages. No imputation will be performed and missing data will be treated as missing.

Aim 1: To determine feasibility and safety of a pragmatic urine alkalinization protocol for the prevention of AKI

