Primary feasibility outcome will be the proportion of patients treated who achieve >50% of urine measurements pH \geq 7.2 over the duration of treatment. Following specific adverse events will be monitored – hypokalemia (K<3.0meq/L), hypocalcemia (Ca<7.6mg/dL when corrected for albumin), Hypernatremia (Na>155meq/L), Volume overload (gaining weight >10% from admission weight during the protocol time-period, need for positive pressure ventilation or intubation due to volume overload), arrhythmias due to hypokalemia or hypocalcemia. To assess safety and feasibility, summary statistics including frequency, mean, standard deviation, median and interquartile range will be provided as applicable. Baseline data will be summarized comparing treatment groups over time. Chi-square/t-test will be used to compare the difference between treatment groups. Mixed model /ANCOVA will be used for repeated measurements over time.

As per the requirements of COE, a Data Safety Monitoring Board (DSMB) has been established that includes [name] [name], [name], [name] and [name] [name]. The DSMB will meet to review any adverse events after 5 and 25 patients have been recruited. In addition, as per the requirements of COE, the DSMB will meet to review any adverse events after the first 5 patients randomized to the interventional drug (open label arm) have been recruited and completed the study.

Aim 2: To determine the efficacy of urine alkalinization for prevention of AKI

Primary efficacy outcome will be the number of days alive and free of stage 2-3 AKI (up to 28) in each group. Secondary endpoints will include the proportion of patients developing stage 2-3 AKI (or stage 3 if already at stage 2 at enrollment); ventilator-free days to 28 and hospital-free days to 60. For AKI-free, ventilator-free, and hospital-free days, zero truncated negative binomial models will be implemented.

Severe AKI will be considered as binary outcome. Multivariable logistic regression will be used to assess the overall odds associated with treatment adjusted by baseline covariates (age, demographics, baseline renal function). Random forest decision tree regression method will be implemented to assess patient variable importance towards the outcome. Hazard will be assessed using cox proportional hazard model.

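### Ventilator-free and hospital-free days are compared with no adjustment or stratification for ventilation at entry, which gives up some power and leaves these secondary endpoints exposed to chance imbalance at 20 per arm

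*Combined protocol and SAP*

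**What the plan says.** All references are to section B.5 (Approach) of the combined protocol and SAP.

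- **Endpoints.** Under Statistical analysis, Aim 2, the secondary endpoints include "ventilator-free days to 28 and hospital-free days to 60".
- **Model.** The analysis of these counts is one sentence: "For AKI-free, ventilator-free, and hospital-free days, zero truncated negative binomial models will be implemented". No covariate is named.
- **Covariates.** The one Aim 2 list is in the logistic regression sentence for severe AKI: "treatment adjusted by baseline covariates (age, demographics, baseline renal function". It contains nothing respiratory. The mixed model/ANCOVA sentence is under Aim 1 and concerns repeated measurements.
- **Allocation.** Study design reads "Open-label randomized trial (1:1) comparing urine alkalinization to standard care". No stratification factor is given.
- **Population.** Table 1 requires "Admission to ICU or step-down units at WVU" and neither requires nor excludes ventilation. The Aim 1 adverse events include "need for positive pressure ventilation or intubation due to volume overload", so starting ventilation during the study is foreseen for at least some patients.
- **Data.** Data collection lists demographics, comorbidities, medications and "Data about renal function (creatinine, urine output, daily ins and outs), basic metabolic panel, blood gas". Ventilation status at entry is not named.

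**The concern.** A patient on a ventilator at randomisation starts losing ventilator-free days at once. A patient who survives and is never ventilated scores 28. Entry status therefore acts much like a baseline value of this outcome. For hospital-free days a link is plausible, but it is not built into the definition.

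Leaving out such a variable has two consequences. Variation between ventilated and unventilated patients stays in the error term, so a true difference is harder to detect. And if one arm happens to start with more ventilated patients, the unadjusted difference moves with that imbalance. With 20 per arm, sizeable imbalances are common. The trial is also open-label, so a covariate chosen after the data are seen would carry less weight than one named now.

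**Working it through.** **1. The plan's own figure.** Sample size determination gives 16 per group for 10 ± 5 versus 15 ± 5 days. Alpha and power are not stated; I assume two-sided 0.05 and 80%.

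n = 2 × (1.96 + 0.84)² × 5² / 5² = 15.7, rounded up to 16. This reproduces. It concerns days alive without stage 2-3 AKI, so it gives neither an SD nor an effect for the two endpoints at issue and does not change.

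**2. Chance imbalance.** Inputs: 20 per arm (documents); 20 of 40 ventilated at entry (assumed). The number ventilated in one arm is hypergeometric, P(k) = C(20,k) × C(20,20−k) / C(40,20).

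- 12 versus 8 or worse: 1 − P(9) − P(10) − P(11) = 1 − 0.205 − 0.248 − 0.205 = 0.34.
- 13 versus 7 or worse: 0.34 − P(8) − P(12) = 0.343 − 0.115 − 0.115 = 0.11.

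If instead each patient is independently ventilated with probability 0.5, the arms differ by at least 4 patients with probability 0.27; with probability 0.3 or 0.7, it is 0.23.

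**3. Size of the shift.** Shift = (difference in proportion ventilated) × (gap in mean ventilator-free days). A 4-patient imbalance is 4/20 = 0.20. The gap is not in the documents. For assumed gaps of 4, 8 and 12 days the shift is 0.8, 1.6 and 2.4 days.

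**4. Precision, on a linear scale.** Assume half are ventilated and the within-group SD is 8 days. Then R² = 0.25g² / (0.25g² + 64), and the detectable difference at 80% power is 2.80 × SD × √(2/20).

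| Gap g (days) | R² | Unadjusted | Adjusted |
|---|---|---|---|
| 4 | 0.06 | 7.3 days | 7.1 days |
| 8 | 0.20 | 7.9 days | 7.1 days |
| 12 | 0.36 | 8.9 days | 7.1 days |

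Equivalent sample size per arm is 20 / (1 − R²). Power, for a comparison with 80% unadjusted, is Φ(2.80/√(1 − R²) − 1.96).

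| R² | Worth per arm | Power |
|---|---|---|
| 0.05 | 21 | 82% |
| 0.10 | 22 | 84% |
| 0.20 | 25 | 88% |
| 0.30 | 29 | 92% |
| 0.40 | 33 | 95% |

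**5. Simulation** (normal outcomes, SD 8, each patient ventilated with probability 0.5, 20 per arm; it shows direction and size and does not fit the planned count model).

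- No treatment effect: type I error is about 5% overall, with or without adjustment.
- No treatment effect, given an imbalance of at least 4 patients: 8.9% (gap 8) or 12.0% (gap 12) unadjusted, about 5% adjusted.
- True effect of 8 days: power 79% unadjusted versus 86% adjusted (gap 8), and 69% versus 86% (gap 12).

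**6. The planned model.** A zero-truncated distribution gives no probability to 0. A patient ventilated through day 28 scores 0, so adding a covariate to the planned model would not be enough.

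**The case against.** The strongest case against is that this is good practice left out rather than an error, on two secondary endpoints of a 40-patient trial sized on another outcome. Randomisation makes the unadjusted comparison valid, and its interval already allows for chance imbalance. Every magnitude rests on assumption: the documents give no share ventilated, no distribution and no SD for these endpoints. At R² = 0.05 the gain is about one patient per arm. All of that stands, and it limits the weight of the point. It does not remove it, because the remedy costs very little.

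A reader might go further in four ways that the documents do not support.

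- *Entry ventilation is the strongest determinant of both endpoints.* Nothing in the documents ranks determinants. The link is structural for ventilator-free days only.
- *The unadjusted analysis is biased, or creates false positives.* Overall type I error stays near 5%; only the error conditional on an imbalance rises.
- *Adjustment narrows the interval whatever the model.* The 1/(1 − R²) gain is a linear-model result. In a proportional-odds model the adjusted odds ratio is conditional and its standard error usually grows; the benefit is in power.
- *The loss is known to be large.* A 15-day gap (assumed means 6.5 versus 21.5) would give R² of about 0.40 with half ventilated and a 3-day shift from a 12 versus 8 split. That is one favourable assumption. With an SD of 11.9 in that scenario, the standard error is 11.9 × √(2/20) = 3.8 days, so the shift is about 0.8 standard errors.

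The planned pooling with the second centre does not answer the point, since it is described for AKI rates and survival.

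**Conclusion.** The gap is real under either reading of the covariate sentence: extending the logistic model's list to the day counts would still bring in no respiratory variable. Leaving entry ventilation out gives up power and leaves these comparisons open to an imbalance of 12 versus 8 or worse in about one randomisation in three, if half the patients are ventilated at entry.

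The size of the loss cannot be fixed from the documents. It is small if entry ventilation explains about 5% of the variance and material from about 20%. The figures are for ventilator-free days or a generic linear outcome; for hospital-free days the prognostic link itself is assumed. A mix of ventilated and unventilated patients at entry is allowed by the criteria and likely, but not stated. The primary efficacy outcome and its sample size are untouched, so the effect on the main conclusion is limited.

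**What to change.** 1. Add ventilation at randomisation (yes/no) to the data collection list, with a definition of what counts as ventilated.
2. State in the Aim 2 analysis that ventilator-free and hospital-free days will be compared with this variable as stratum or covariate, using a method that accommodates zeros in place of the zero-truncated model. A van Elteren test stratified by entry ventilation, or a proportional-odds model with entry ventilation as a covariate, would do.
3. Report the unadjusted result as a sensitivity analysis.
4. In the same edit, define how deaths are scored for these two endpoints, which the plan leaves open.

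The cost is one data field and a short SAP change, with no effect on sample size. If proportional odds is chosen, the odds ratio is conditional on ventilation status rather than marginal, and the report should say so.

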Aim 1: To determine the feasibility and safety of a pragmatic urine alkalinization protocol for the prevention of AKI in patients testing positive for COVID-19. Primary outcome will be the proportion of patients treated who achieve >50% of urine measurements above pH 7.0 over the duration of intervention. Other outcomes will include protocol adherence and provider acceptance.

Aim 2: To determine the effectiveness of urine alkalinization for prevention of AKI in patients testing positive for COVID-19. Primary outcome will be the number of days alive and free of stage 2-3 AKI (up to 28) in each group. Secondary endpoints will include the proportion of patients developing stage 2-3 AKI (or stage 3 if already at stage 2 at enrollment); ventilator-free days to 28 and hospital-free days to 60.

Completion of this study will provide clinically relevant information regarding the role of urine alkalinization in prevention of AKI associated with COVID-19. This will have wide ranging implications for patients with COVID-19. [name], Professor and Vice Chair for Research in the Department of Critical Care Medicine at the University of Pittsburgh, a co-I on this application and my co-mentor for the WVCTSI research scholar application is also in the process of conducting this study at the University of Pittsburgh. At the completion of this study, the results from both centers (WVU and UPitt) will then be pooled and changes in AKI rates, and survival will be examined among patients with COVID-19.

B. RESEARCH STRATEGY (5 pages max)

1. Background

Severe Acute Respiratory Syndrome Coronavirus 2 (SARS-CoV-2) is rapidly spreading around the world. The current outbreak of infections with SARS-CoV-2 is termed Coronavirus Disease 2019 (COVID-19). Two other coronavirus infections, SARS in 2002-2003 and Middle East Respiratory Syndrome (MERS) in 2012, both caused severe respiratory syndrome in humans. All 3 of these emerging infectious diseases are caused by β -coronaviruses. COVID-19, declared a pandemic by the World Health Organization on Mar 11, 2020, is associated with high mortality in patients admitted to intensive care units (ICUs) [1]. Though COVID-19 primarily affects lungs leading to Acute Respiratory Distress Syndrome (ARDS), other life-threatening acute organ dysfunctions such as acute kidney injury (AKI) and cardiomyopathies are also commonly described.

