Sample size determination: The study will be powered to achieve a 50% increase in the number of days alive and free of stage 2-3 AKI to day 28. We hypothesis an increase from 10 +/- 5 days to 15 +/- 5 days. The sample size needed to achieve this difference is 16 patients per group. We plan to enroll 20 patients per group for a total sample size of 40 patients. [name], Professor of Critical Care Medicine at the University of Pittsburgh and a co-investigator on this application is working towards a similar trial at the University of Pittsburgh (see attached letter of

support). The results from both these studies will then be pooled and changes in AKI rates, and survival will be examined.

Relevance to the current COVID-19 pandemic

There are at least four reasons why this study will have an important impact. First, when severe AKI does occur, mortality is very high.[6, 7] Preventing early AKI may reduce severe AKI as the disease progresses. Second, AKI has considerable effects on the immune system reducing a variety of immune functions[28] and hence might contribute to reduced host response. Third, this is unlikely to be the last β-coronavirus outbreak and different strains may cause even more AKI. Finally, the results of this study would provide critical proof of concept data that could be used to design other therapies to reduce viral RBD affinity. For example, alveolar pH could also be manipulated. Showing feasibility with this safe and available strategy could be the first step toward other related efforts.

C. REFERENCES

2. **KDIGO Clinical Practice Guideline for Acute Kidney Injury** [<https://kdigo.org/wp-content/uploads/2016/10/KDIGO-2012-AKI-Guideline-English.pdf>]

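### The zero-truncated negative binomial model planned for the three day-count endpoints cannot include patients with 0 days, although 0 is possible on all three

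*Combined protocol and SAP*

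**What the plan says.** Section 5 (Approach), Statistical analysis, Aim 2, defines the endpoints. "Primary efficacy outcome will be the number of days alive and free of stage 2-3 AKI (up to 28) in each group." The secondary endpoints include "ventilator-free days to 28 and hospital-free days to 60". One model is named for all three: "For AKI-free, ventilator-free, and hospital-free days, zero truncated negative binomial models will be implemented."

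These parts of the document bear on whether 0 can occur:

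- Table 1 requires admission to an ICU or step-down unit. Its only AKI exclusion is "Stage 3 AKI by KDIGO criteria". Aim 2 itself provides for patients already at stage 2 when enrolled. ECMO is excluded; mechanical ventilation is not.
- The Background describes mortality among ICU patients as high but gives no rate.
- On missing data the plan says: "No imputation will be performed and missing data will be treated as missing." It gives no rule for zeros or for scoring death.
- Sample size determination assumes, for the primary outcome: "We hypothesis an increase from 10 +/- 5 days to 15 +/- 5 days."

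**The concern.** A zero-truncated distribution starts at 1. If a data set contains a 0, the likelihood is undefined unless that patient is removed. The plan describes no hurdle or zero-inflated part that would bring such patients back.

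The patients removed have the worst outcomes, and those outcomes arise after randomisation. The arms that remain are no longer the randomised arms. If treatment changes how many patients die in hospital or never come off the ventilator, the model does not see that part of the effect, whether it is benefit or harm. This is the only model named for the primary efficacy outcome and for two secondary endpoints.

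**Working it through.** **1. Can 0 occur?**

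| Endpoint | How a patient scores 0 |
|---|---|
| Days alive and free of stage 2-3 AKI (to 28) | Enters at stage 2 and never improves; more often if death is scored 0 |
| Ventilator-free days (to 28) | Ventilated from enrolment to death or to day 28 |
| Hospital-free days (to 60) | Still in hospital at day 60 or, on the usual scoring, dies in hospital |

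All three are possible under Table 1 and the endpoint definitions.

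**2. The plan's own sample size.** Inputs: difference 5 days, SD 5. Assumed, because not stated: two-sided 5% level and 80% power. n per group = 2 × (1.960 + 0.842)² × 5² / 5² = 15.7, so 16, as the plan says. This is a comparison of two normal means, not the planned count model. By the same approximation, power is 80.7% with 16 per group and 88.5% with 20.

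**3. Zeros implied for the primary outcome.**

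- Negative binomial: k = mean² / (SD² − mean) and P(0) = (k/(k + mean))^k. Control: k = 100/15 = 6.67, P(0) = 0.2%. Treatment: k = 225/10 = 22.5, P(0) = 0.001%.
- Rounded normal: P(0) = Φ((0.5 − mean)/5). Control: Φ(−1.9) = 2.9%. Treatment: Φ(−2.9) = 0.2%.
- Upper limit for any distribution with these moments: SD²/(SD² + mean²). Control: 25/125 = 20%. Treatment: 25/250 = 10%.

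In 400 simulated trials of 20 against 20 at the planning figures, the truncated model gave a ratio of 1.48 (planned 15/10 = 1.50). It rejected in 83% of trials, against 82% for a rank test.

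**4. If primary zeros are more common.** With overall means held at 10 and 15, the ratio among non-zero patients is 1.50 × (1 − p_control)/(1 − p_treatment):

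| Zeros, control vs treatment | Ratio among non-zero patients (true 1.50) |
|---|---|
| 2.9% vs 0.2% | 1.46 |
| 5% vs 0% | 1.425 |
| 10% vs 0% | 1.35 |
| 20% vs 0% (mathematical limit) | 1.20 |
| 0% vs 10% (mathematical limit) | 1.67 |
| equal shares | 1.50 |

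**5. Secondary endpoints.** The documents give no zero shares, so those below are assumed. Non-zero days have the same distribution in both arms: uniform 10-55 for hospital-free days and 5-27 for ventilator-free days. The true ratio is then (1 − p_treatment)/(1 − p_control), for example 0.8/0.6 = 1.33. Each row rests on 300 simulated trials of 20 against 20.

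| Endpoint | Zeros, control vs treatment | True ratio | Truncated model |
|---|---|---|---|
| Hospital-free | 40% vs 20% | 1.33 | 1.01 |
| Hospital-free | 20% vs 40% | 0.75 | 1.02 |
| Hospital-free | 20% vs 10% | 1.13 | 0.99 |
| Hospital-free | 10% vs 20% | 0.89 | 1.00 |
| Ventilator-free | 40% vs 20% | 1.33 | 1.00 |
| Ventilator-free | 20% vs 40% | 0.75 | 1.02 |

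With 20,000 per arm the model gives 0.99 to 1.01 in every row. At 40% vs 20%, 20 × 0.6 + 20 × 0.8 = 28 of 40 patients are kept.

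The direction can also reverse. With 50% vs 20% zeros and non-zero means of 18 and 15, the true ratio is (0.8 × 15)/(0.5 × 18) = 1.33, while the fitted ratio is 0.84.

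**The case against.** The strongest reply is that the primary outcome is hardly affected. At the planning figures zeros are rare, the fitted ratio is close to 1.50, and the model has the same power as a rank test to within about two percentage points. This stands, provided the planning figures hold. They are hypotheses, and neither the number of stage 2 entrants nor the scoring of death is fixed. The 1.20 and 1.67 cases are limits, reached only if every non-zero patient has the same value (12.5 days in control, 16.7 on treatment). They bound the problem and are not forecasts.

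A second reply is that the secondary scenarios put the whole effect into the zeros, so a fitted ratio near 1 follows by construction. That is also fair. If treatment lengthens non-zero days as well, the model still sees part of the effect. With 40% vs 20% zeros and non-zero days uniform on 5-45 and 15-55, the true ratio is (0.8 × 35)/(0.6 × 25) = 1.87. The fitted ratio is 1.42, with rejection in 51% of trials against 60% for a rank test. The effect is attenuated rather than lost, but the estimate is still not that of the randomised comparison.

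Third, other analyses retain some of the events: the proportion with stage 2-3 AKI, logistic regression for severe AKI, a Cox model whose outcome is not named, and the pooled survival analysis. The chi-square and t-tests are listed under Aim 1. None of these compares the three day counts in all randomised patients.

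The wording may be a slip for a zero-inflated or hurdle model. The text does not say so, and it would need correcting in that case too.

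**Conclusion.** The concern holds. That the model cannot include 0, and that 0 can occur on all three endpoints, follows from the document alone. The size of the distortion depends on zero shares that the document does not give.

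For the primary outcome the distortion is small at the planning figures, and grows if stage 2 entrants are common or death is scored 0. For ventilator-free and hospital-free days it is likely to be larger: every patient starts in hospital, many may start on a ventilator, and no planning figures limit the zeros. Under the assumed 40% and 20% shares with equal non-zero distributions, a one-third increase or a one-quarter decrease in mean days both appear as no effect.

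For the primary outcome the problem is bias rather than sample size: even at the 20% limit, 16 of 20 control patients would be expected to remain, the number the plan requires. The rule should be corrected before analysis.

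**What to change.** Replace the model sentence with:

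> AKI-free, ventilator-free and hospital-free days will be compared in all randomised patients, zeros included, with a proportional-odds ordinal model (its unadjusted score test corresponds to the Wilcoxon rank-sum test). The common odds ratio will be reported with its 95% CI and, descriptively, the difference in means with a bootstrap 95% CI.

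Add one sentence stating, for each outcome, how death is scored.

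No new data or patients are needed. At the planning figures the rank test lost about one point of power (82% against 83%); this was simulated with the Mann-Whitney test, not the ordinal model itself. The main drawback is that the result becomes an odds ratio, so the planned 50% increase in days appears only through the descriptive means. A hurdle model or an untruncated count model would also keep the zeros and could be chosen if a ratio of days matters more; either would have to be specified in full.

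The gain is an estimate that includes every patient, not high power. In the 40% vs 20% scenarios the rank test on all 40 patients rejects in only 17-19% of trials.
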